5.3 OTHER

5.3.1 Other endpoint(s)

This section is not applicable in this study.

Proprietary confidential information.

© 2017 Boehringer Ingelheim International GmbH or one or more of its affiliated companies. All rights reserved.
This document may not - in full or in part - be passed on, reproduced, published or otherwise used without prior written permission.

5.3.2 Other assessment(s)

5.3.2.1 Physical examination, height, body weight, and performance status

A general physical examination will be performed at screening, at the end of each infusion in cycles 1 and 2, 15 days after start of infusion in cycle 1 and 21 days after start of infusion in cycle 2 as well as at the end of the treatment. The same investigator should perform this examination. Physical examination will include measurement of height and body weight and the evaluation of the ECOG performance score. Height will be documented only once at screening. Weight and ECOG score will also be assessed when volasertib treatment is started and at the end of the treatment. ECOG will also be assessed at the last visit of each cycle.

After approval of Protocol Revision 3, physical examinations, weight, and ECOG performance score should be done as medically indicated at discretion of the investigator. The results are not required to be entered in the eCRF; documentation in the source data is sufficient. In case of findings that are qualifying as an (S)AE the respective (S)AE will be reported (eCRF and SAE form if applicable).

5.3.2.2 Demographics and history

Demographics (sex, birth date, race), information on smoking and alcohol status, and baseline conditions will be collected during the screening.

History of tumour will also be obtained. The type of tumour, the date of first histological diagnosis (month and year may be sufficient), and the primary tumour site will be reported into the eCRF. The differentiation grade (not specified, poorly differentiated, moderately differentiated, well differentiated), the number and location of metastatic sites as well as the stage according to the tumour, (lymph) node, metastasis (TNM) classification and the [REDACTED]

[REDACTED] / American Joint Committee on Cancers (AJCC) classification will be provided as obtained at diagnosis. It will also be recorded whether visceral involvement, bone involvement or soft tissue involvement is present (yes, no, unknown). Previous surgery will be reported. Previously administered radio-, chemo-, immuno-, molecular-targeted, and hormone therapy will be reported including start and end dates (month and year may be sufficient), the therapy protocol with the number of cycles (chemo-, immunotherapy), the best response obtained (complete response, partial response, stable disease, progressive disease, unknown) as well as whether the therapy was given as neoadjuvant, adjuvant, or palliative therapy. Concerning previous radiotherapy the total radiation dose and radiation field will be recorded.

5.3.2.3 Concomitant diagnoses and/or therapy

Concomitant diagnoses and/or therapies present at study entry and/or during screening will be recorded in the eCRF.

Proprietary confidential information.

© 2017 Boehringer Ingelheim International GmbH or one or more of its affiliated companies. All rights reserved.
This document may not - in full or in part - be passed on, reproduced, published or otherwise used without prior written permission.

5.4 APPROPRIATENESS OF MEASUREMENTS

The assessments which will be performed in this study are standard, and generally recognised as being reliable, accurate and relevant.

5.4.1 Timing of assessments

Date and exact clock time of drug administration as well as of PK sampling must be recorded. The designation “before” on study Day 1 refers to the time period of 2 hours prior to drug administration, i.e. study measurements and assessments scheduled to occur “before” must be performed and completed within 2 hours prior to drug administration. For data management purposes, this pre-dose period is referred to in the [flow chart](#) and [section 5.2](#) as -0:30 h.

A time window of +/- 5 % of the time from dosing to scheduled sample timepoint will be allowed for PK blood sampling. Nominal times should be adhered to as closely as possible. PK sampling time deviations of more than 5% will be identified and their handling discussed no later than at the last RPM before preliminary snapshot generation.

The duration of the volasertib infusion (planned 120 min) as well as interruptions if applicable will be documented (start and end time of the infusion) in the eCRF. Every attempt will be made to adhere to an infusion time of 120 min for volasertib with a constant infusion rate.

In the event assessments are planned for the same scheme time, the order of the assessments should be arranged in such a way that ECG will be performed before vital signs, followed by blood sampling. Blood sampling times should be adhered to as closely as possible.

Proprietary confidential information.

© 2017 Boehringer Ingelheim International GmbH or one or more of its affiliated companies. All rights reserved.
This document may not - in full or in part - be passed on, reproduced, published or otherwise used without prior written permission.

5.5 DRUG CONCENTRATION MEASUREMENTS AND PHARMACOKINETICS

Blood for pharmacokinetic analysis will be collected at specified time points during the first and the second treatment cycle (see FlowChart) to determine the plasma concentration of volasertib, its clinical relevant metabolite CD 10899 (if feasible) and itraconazole. Further exploratory analysis for identification of drug metabolites could be done if applicable. If these additional analyses are performed, the results will be reported separately. The actual sampling date and time for blood samples will be documented in the eCRF. These actual sampling times will be used for determination of pharmacokinetic parameters.

Please note that for a valid PK analysis, it is of utmost importance to document the exact clock time of trial medication administration. The duration of the volasertib infusion (planned 2 hours) will be documented (start and end time of the infusion as well as interruptions) in the eCRF. Every attempt will be made to adhere to an infusion time of 2 hours for volasertib with a constant infusion rate.

5.5.1 Pharmacokinetic endpoint(s)

Pharmacokinetic parameters will be evaluated by means of noncompartmental analysis. The derivation of pharmacokinetic parameters is described in detail in the internal SOP 001-MCS-36-472_RD-01.

Primary endpoints (volasertib and CD 10899):

[figure not shown]
- maximum measured plasma concentration (C_{max})
- area under the plasma concentration-time curve over the time interval from zero to the last quantifiable drug plasma concentration after dose administration (AUC_{0-tz})

Secondary endpoint (volasertib and CD 10899):

- area under the plasma concentration-time curve over the time interval from zero extrapolated to infinity ($AUC_{0-\infty}$)

Proprietary confidential information.

© 2017 Boehringer Ingelheim International GmbH or one or more of its affiliated companies. All rights reserved.
This document may not - in full or in part - be passed on, reproduced, published or otherwise used without prior written permission.

All pharmacokinetic measurements will be performed only in first two treatment cycles.

5.5.2 Methods of sample collection

Actual date and time of blood collection together with the patient number should be recorded in the eCRF.

5.5.2.1 Blood sampling

During the trial PK blood samples will be collected to determine the concentration of volasertib, its metabolite CD 10899 (if feasible) and itraconazole in plasma.

PK blood samples before start of infusion and shortly before end of infusion will be taken from a forearm vein contralateral to the infusion site. For patients having a central venous catheter, volasertib may be administered using this device and PK blood samples should be obtained from either forearm. For planned times please refer to the [Flow Chart](#).

Cycle 1:

For quantification of plasma concentrations of volasertib, the metabolite CD 10899, and itraconazole, around 4 mL of venous blood will be taken in a potassium EDTA (ethylenediaminetetraacetic acid)-anticoagulant blood drawing tube (e.g. Vacutainer® or Monovette) at the time points specified in the FlowChart.

The sampling tubes have to be mixed immediately with the anticoagulant by gently inverting about 10 times. Vigorous shaking should be avoided to prevent haemolysis. The whole blood is to be centrifuged at 4-25°C at approximately 3000 rpm (~2100 g) for at least 15 minutes. Centrifugation should be done within 60 min after sampling. The blood samples should be stored at room temperature or below until centrifugation.

From each blood sample, transfer immediately three aliquots of EDTA plasma (at least 500 µL each, aliquot 1 for volasertib/CD 10899, aliquot 2 for itraconazole, and aliquot 3 as

Proprietary confidential information.

© 2017 Boehringer Ingelheim International GmbH or one or more of its affiliated companies. All rights reserved.
This document may not - in full or in part - be passed on, reproduced, published or otherwise used without prior written permission.

back-up) into carefully and unique labelled cryovials. Blood sample should be transferred always into three aliquots independent of analysis that will be performed for this time point. Please check the patient number and planned sampling time. The visit, the exact time (hh:mm, 24 h-clock time) and date (month in letter) of sampling are to be recorded in the eCRF.

[figure not shown]
Cycle 2:

For quantification of plasma concentrations of volasertib and its metabolite CD 10899 around 4 mL of venous blood will be taken in a potassium EDTA (ethylenediaminetetraacetic acid)-anticoagulant blood drawing tube (e.g. Vacutainer® or Monovette) at the time points specified in the FlowChart.

The sampling tubes have to be mixed immediately with the anticoagulant by gently inverting about 10 times. Vigorous shaking should be avoided to prevent haemolysis. The whole blood is to be centrifuged at 4-25°C at approximately 3000 rpm (~2100 g) for at least 15 minutes. Centrifugation should be done within 60 min after sampling. The blood samples should be stored at room temperature or below until centrifugation.

From each blood sample, transfer immediately two aliquots of EDTA plasma (at least 600 µL each, aliquot 1 for volasertib/CD 10899 and aliquot 2 as back-up) into carefully and unique labelled cryovials. Please check the patient number and planned sampling time. The visit, the exact time (hh:mm, 24 h-clock time) and date (month in letter) of sampling are to be recorded in the eCRF.

The plasma samples have to be stored at -20°C or below at the clinical site until shipment on dry ice to the analytical laboratory. They also will be stored at the analytical laboratory at -20°C or below until analysis.

Proprietary confidential information.

© 2017 Boehringer Ingelheim International GmbH or one or more of its affiliated companies. All rights reserved.
This document may not - in full or in part - be passed on, reproduced, published or otherwise used without prior written permission.

5.6 BIOMARKER(S)

During the course of the study no biomarker will be determined.

5.6.1 Endpoints based on biomarker(s)

This section is not applicable in this study.

5.6.2 Methods of sample collection

This section is not applicable in this study.

5.6.3 Analytical determinations

This section is not applicable in this study.

5.7 PHARMACODYNAMICS

This section is not applicable in this study.

5.7.1 Pharmacodynamic endpoints

This section is not applicable in this study.

5.7.2 Methods of sample collection

This section is not applicable in this study.

5.8 PHARMACOKINETIC - PHARMACODYNAMIC RELATIONSHIP

In this study, no pharmacokinetic-pharmacodynamic relationship will be studied.

Proprietary confidential information.

© 2017 Boehringer Ingelheim International GmbH or one or more of its affiliated companies. All rights reserved.
This document may not - in full or in part - be passed on, reproduced, published or otherwise used without prior written permission.

6. INVESTIGATIONAL PLAN

6.1 VISIT SCHEDULE

The patients will stay at the investigator site from the evening before first itraconazole administration (day -4) until day 4 of the first cycle as well as from the day before intravenous infusion of volasertib until 72 hours after start of infusion of the second cycle (day -1 until day 4). Ambulatory visits will happen 168 hours (day 8), 336 hours (day 15) and 504 hours (day 22) after start of infusion, where the last visit may coincide with day 1 of consecutive treatment cycles. In this case the blood sample for PK has to be taken before administration of the study drug.

Procedures will be performed as outlined in the [flow chart](#). In third and subsequent treatment cycles the patient will visit the investigator at regular intervals as specified in the flow chart (visit 2 and 3 are optional visits at the investigator's discretion) for determination of safety laboratory parameters, recording of adverse events and additional procedures as outlined in the flow chart. If a patient misses a visit and the patient reports to the investigator between this and the next scheduled visit, the missed visit should be performed with the actual date and the reason should be given for the delayed visit. The next visit, however, should take place as scheduled relative to the first administration of the trial drug in the treatment cycle.

6.2 DETAILS OF TRIAL PROCEDURES AT SELECTED VISITS

6.2.1 Screening and run-in period

The screening phase (screen visit) i.e. after informed consent and prior to the first administration of the trial drug may be up to 14 days in duration. After written informed consent has been obtained, the investigator should perform the procedures required for screening within 14 days and prior to the first treatment within the trial.

The following will be obtained and / or performed:

- Informed consent and patient information
- Demographics (sex, birth date, race)
- Medical history (oncological, relevant non-oncological, smoking status, alcohol consumption)
- Physical examination including body height, weight, vital signs and ECOG performance score
- Patient eligibility (inclusion and exclusion criteria)
- Concomitant therapy
- Drugs of abuse in urine and alcohol breath test
- Resting 12-lead ECG
- Safety laboratory (no repeat examination in case a safety laboratory investigation has been performed within 14 days before the screening visit), including urine dipstick

Proprietary confidential information.

© 2017 Boehringer Ingelheim International GmbH or one or more of its affiliated companies. All rights reserved.
This document may not - in full or in part - be passed on, reproduced, published or otherwise used without prior written permission.

- Coagulation parameters
pregnancy test for women of childbearing potential - women of childbearing potential (premenopausal female patient) is defined as the female patient who is not surgically sterilised by hysterectomy or bilateral tubal ligation, or post-menopausal for at least 12 months.

6.2.2 Treatment period

6.2.2.1 First Treatment Cycle

The first treatment cycle will be performed under partially hospitalised conditions: For detailed timing of the assessments please refer to the [flow chart](#).

- Physical examination
- Review of in- and exclusion criteria
- ECOG performance score
- Body weight
- ECG
- Vital signs
- Oral administration of itraconazole in 24 hour intervals
- Intravenous administration of volasertib
- Blood sampling for determination of volasertib, CD 10899 [REDACTED] concentrations in plasma
- Blood sampling for pharmacogenetics
- Safety lab parameters (without urinalysis)
- Coagulation parameters
- Occurrence of AEs since enrolment
- Changes in concomitant therapy
- Clinical tumour assessment
- Review of patient eligibility for repeated treatment cycles

6.2.2.2 Second Treatment Cycle

The second treatment cycle will be performed under partially hospitalised conditions: For detailed timing of the assessments please refer to the [flow chart](#).

- Physical examination
- Review of in- and exclusion criteria
- ECOG performance score
- Body weight
- ECG
- Vital signs
- Intravenous administration of volasertib
- Blood sampling for determination of volasertib and CD 10899 concentrations in plasma

Proprietary confidential information.

© 2017 Boehringer Ingelheim International GmbH or one or more of its affiliated companies. All rights reserved.
This document may not - in full or in part - be passed on, reproduced, published or otherwise used without prior written permission.

- Safety lab parameters (without urinalysis)
- Coagulation parameters
- Occurrence of AEs since enrolment
- Changes in concomitant therapy
- Clinical tumour assessment
- Review of patient eligibility for repeated treatment cycles
- pregnancy test for women of childbearing potential - women of childbearing potential (premenopausal female patient) is defined as the female patient who is not surgically sterilised by hysterectomy or bilateral tubal ligation, or post-menopausal for at least 12 months.

6.2.2.3 Subsequent treatment cycles (non-DDI)

After implementation of Protocol revision 3, safety laboratory parameters and additional investigations (body weight, ECOG, vital signs, physical examination etc) at subsequent treatment cycles will be done as medically indicated at discretion of the investigator.

Investigator will continue recording ECG prior and at the end of volasertib infusion to ensure patient safety. For this purpose investigator will use local ECG machine, centralized ECG analysis will be discontinued. Findings that are qualifying as an (S)AE the respective (S)AE will be reported (eCRF and SAE form if applicable).

Clinical response assessment will be done after every cycle, radiological assessment at the investigator's discretion. After implementation of the Protocol revision 3, this efficacy data will be recorded in the source data only; documentation in the eCRF is not required.

6.2.2.3.1 Visit 1 (Day 1 of volasertib administration)

On the treatment day, the following will be obtained and / or performed:

- Physical examination
- ECOG performance score
- Body weight
- ECG
- Vital signs
- Clinical tumour assessment
- Safety lab parameters (without urinalysis)
- Coagulation parameters
- Administration of volasertib
- Occurrence of AEs since enrolment
- Changes in concomitant therapy

Proprietary confidential information.

© 2017 Boehringer Ingelheim International GmbH or one or more of its affiliated companies. All rights reserved.
This document may not - in full or in part - be passed on, reproduced, published or otherwise used without prior written permission.

6.2.2.3.2 Visits 2 and 3 (day 8 and 15)

Visits 2 and 3 are optional from the second cycle onwards; the visits may be omitted at the discretion of the investigator. At these visits, the following will be obtained and / or performed:

- Vital signs
- Occurrence of AEs since last visit
- Changes in concomitant therapy
- Safety lab parameters (without urinalysis)

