9. Can be taken also at any later time point from those patients who received at least first cycle of volasertib.
10. Analysed for itraconazole only
11. Analysed for volasertib and CD 10899 metabolite only
12. PK sampling should be taken just before itraconazole intake

Proprietary confidential information.

© 2017 Boehringer Ingelheim International GmbH or one or more of its affiliated companies. All rights reserved.
This document may not - in full or in part - be passed on, reproduced, published or otherwise used without prior written permission.

TREATMENT CYCLE 2 (volasertib without itraconazole)

Visit	Day	Planned Time [h:min]	Approximate clock time of actual day [h:min]	Event and comment	Safety Laboratory (S), Coagulation (C)	PK _{plasma} volasertib and CD 10899	Vital signs (BP and PR), ECG (digital, triplicate)	Adverse events/ Con. med
1	-1	-17:00	15:00	admission to trial site ^{1,2}				
	1	-0:30 ⁶	7:30	review of in-and exclusion criteria	S	X	X	
		0:00	8:00	start of iv volasertib infusion, ECOG ▲				
		0:30	8:30				X ³	
		1:00	9:00			X	X ³	
		1:45 ⁸	9:45	physical examination		X	X	
		2:00	10:00	▼ end of iv volasertib infusion, ECOG				
		3:00	11:00				X	
		4:00	12:00			X		
		6:00	14:00			X	X ⁷	
		8:00	16:00			X		
		12:00	20:00			X		
	2	24:00	8:00		C	X	X ⁷	
		36:00	20:00			X		
		48:00	8:00			X		
2	8	168:00	8:00	discharge from trial centre		S	X	X ³
3	15	336:00	8:00				X	
4 ⁹	22	504:00	8:00	physical examination, body weight, ECOG, tumour assessment, eligibility for further treatment cycle ⁴	S, C	X	X ³	

1. Patients should be admitted to hospital and stay until day 4 (72h after start of infusion)
2. Pregnancy test in women of childbearing potential
3. Vital signs only
4. Only patients with clinical benefit after volasertib treatment based on investigator's assessment (clinical response, or absence of progression, or symptom improvement) will qualify for further participation in the trial. In case of symptom improvement despite disease progression a repeated cycle may be allowed upon the agreement of the clinical monitor and the investigator.
5. Safety lab includes haematology, and serum biochemistry. For detail see [5.2.3](#). Urinalysis (dipstick) is only performed at screening and EOT.
6. For predose sampling of volasertib and CD 10899 in plasma, metabolic profiling, the time window is 2 hours before start of infusion.
7. ECG only
8. Shortly before end of infusion
9. This visit may co-incide with visit 1 of treatment cycle 3

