Proprietary confidential information.

© 2017 Boehringer Ingelheim International GmbH or one or more of its affiliated companies. All rights reserved.
This document may not - in full or in part - be passed on, reproduced, published or otherwise used without prior written permission.

SUBSEQUENT TREATMENT CYCLES (for patients with clinical benefit)

Study period	Treatment				EOT ¹	FU ²
Visit	V1	V2 ⁶	V3 ⁶	V4 ⁷		
Day	1	8	15	22		
(day range)		(±1)	(±1)	(±2)		
Physical examination ¹⁰	X			X	X	
ECOG performance score ¹⁰	X			X	X	X
Body weight ¹⁰	X			X	X	
Vital signs ¹⁰	X	X	X	X	X	X
ECG	X ³				X	
Tumour assessment ⁸	X			X	X	
Infusion of volasertib	X					
Safety lab parameters ⁴	X	X	X	X	X	
Coagulation parameters ⁴	X			X	X	
Pregnancy test ⁹				X		
Adverse events	X	X	X	X	X	X ²
Concomitant therapy	X	X	X	X	X	
Termination of trial medication					X	
Treatment with any other anti-tumour drug						X
Patient status					X	X
Eligibility for further treatment cycle	X			X		

1. EOT, end of treatment. Assessments which are to be performed at the last visit (when a patient discontinues the study treatment)
2. FU, follow-up. Follow-up visit should be performed 21 days after discontinuation of study drug
3. ECG on visit V1 should be performed according to [5.2.4](#). After approval of the Protocol revision 3, ECG should be performed prior to and at the end of volasertib infusions as single reads using a local ECG machine. No central analysis of ECGs will be performed.
4. Safety lab includes haematology and serum biochemistry. For detail see [5.2.3](#). Urinalysis (dipstick) is only performed at EOT. After approval of the Protocol revision 3, safety laboratory including coagulation parameters should be done only as medically indicated at discretion of the investigator. The results should be recorded in the source data only; documentation in the eCRF is not required.
5. In case adverse events were not yet recovered at the EOT visit or if new AEs occur that are considered drug related
6. Optional visits at the investigators discretion, can be performed by phone as well
7. Visit V4 may coincide with V1 of the following cycle in case the patient continues the study treatment
8. Clinical response assessment after every cycle, radiological assessment at the investigator's discretion. After implementation of the Protocol revision 3, this efficacy data will be recorded in the source data only; documentation in the eCRF is not required.

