4.1.4.3 Subsequent treatment cycles

Patients who are eligible for subsequent cycles (>2) of treatment with volasertib (for criteria to continue treatment see [section 3.3.5](#)) will receive volasertib as long as neither patient nor investigator requests treatment discontinuation. Volasertib will be administered as described for treatment cycle 1.

For possible dose reduction and dose escalation see [sections 4.1.3.1](#) and [4.1.3.2](#).

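### Does the remark that Visits 2 and 3 are optional from the second cycle put the reference-cycle PK samples at risk?

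*Protocol*

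**What the plan says.** Section 6.2.2.3.2 of the Protocol reads: "Visits 2 and 3 are optional from the second cycle onwards; the visits may be omitted at the discretion of the investigator". It is a subsection of 6.2.2.3, whose heading limits it to later cycles outside the drug-drug interaction part. Section 4.1.4.3 shows which cycles those are: "Patients who are eligible for subsequent cycles (>2) of treatment with volasertib".

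Section 6.1 gives the general schedule. After describing the hospital stays of cycles 1 and 2 it states: "Ambulatory visits will happen 168 hours (day 8), 336 hours (day 15) and 504 hours (day 22) after start of infusion". The option comes only afterwards, in brackets, in the sentence that begins "In third and subsequent treatment cycles the patient will visit the investigator at regular intervals as specified in the flow chart".

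The flow charts divide the same way. Footnote 6 of the chart for subsequent cycles says of Visits 2 and 3: "Optional visits at the investigators discretion, can be performed by phone as well". None of the nine footnotes to the cycle 2 chart makes a visit optional.

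**The concern.** The sentence names the wrong cycle. Cycle 2 supplies the denominator of the test/reference ratio, and AUC0-tz is a primary endpoint for both volasertib and CD 10899. If a site took the wording at face value, a patient could lose the 168 h and 336 h samples in the reference period while keeping them in cycle 1. The reference AUC0-tz would then rest on no sample between 72 h and 504 h. The patient might also fail the SAP section 6.3 requirement of complete PK data in both cycles, or stay in the analysis with a less reliable value. Cmax, reached around the infusion, would not change.

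**Working it through.** **1. The passages side by side**

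| Place in the Protocol | Day 8 and day 15 visits in cycle 2 |
|---|---|
| 6.2.2.3.2 | optional, by its wording |
| Heading of 6.2.2.3, and 4.1.4.3 | section covers cycles after the second only |
| 6.1 | scheduled; option attached to cycle 3 onward |
| Cycle 2 flow chart | Visits 2 and 3 listed, no optional footnote |
| Subsequent-cycles flow chart, footnote 6 | option appears here only |
| 5.2.5.1 | vital signs on days 8 and 15 in both of the first two cycles |
| 3.1 | cycle 2 the same as cycle 1 apart from itraconazole |

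The procedure list in 6.2.2.3.2 holds vital signs, adverse events, concomitant therapy and safety laboratory, with no PK sampling. The cycle 2 section, 6.2.2.2, does list PK sampling and refers to the flow chart for timing. The sentence was evidently written for cycles 3 onward.

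Two of these supports are weaker than the rest. Section 3.1 is not literally exact, because the end-of-cycle examination falls on day 15 in cycle 1 and day 22 in cycle 2. In the cycle 2 chart the 336 h row carries a single mark. If it is PK, the chart does not show the vital signs of 5.2.5.1. If it is vital signs, the chart shows no PK at 336 h.

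**2. Reproducing Table 5:1 with the two visits kept**

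- Cycle 1 PK: -24, -0:30, 1, 1:45, 4, 6, 8, 12, 24, 36, 48, 72, 168, 336, 504 h = 15.
- Cycle 2 PK: the same without -24 h = 14.
- Total: 15 + 14 = 29, as printed; 29 × 4.0 mL = 116.0 mL.
- Safety laboratory: screening 1 + cycle 1 days 1, 8, 15 (3) + cycle 2 days 1, 8, 22 (3) = 7, matching 2 + 5.
- Volume: 40.5 + 13.5 + 15.0 + 42.5 + 116.0 + 11.0 = 238.5 mL, as printed.

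**3. With cycle 2 Visits 2 and 3 omitted**

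- PK: 29 − 2 = 27.
- Safety laboratory: 7 − 1 = 6.
- Volume: 238.5 − 2 × 4.0 − 3.0 − 8.5 = 219.0 mL.

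These do not match the table.

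**4. How far the count can be trusted**

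Four of the 29 PK cells are inferred, because the chart is broken in the copy available: cycle 1 at 504 h, and cycle 2 at 72 h, 168 h and 336 h. The cycle 2 168 h row has absorbed the 72 h discharge row, and its marks are shifted. So 25 cells are readable and 4 are filled in. Section 3.1 supports the 504 h sample, and the hospital stay to 72 h supports that one, but the total cannot also prove the cells used to reach it.

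The safety-laboratory count reads its day 8 mark from the same merged row. It is also not decisive alone: if the follow-up draw were a separate one, 1 + 1 + 3 + 2 = 7 is reached without cycle 2 day 8. Only coagulation rules that out, since a separate follow-up draw would give 1 + 1 + 2 + 2 = 6 against the 5 printed. Table 5:1 is consistent with required visits but is not independent proof.

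**5. What a literal reading would expose**

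504 − 72 = 432 h without a sample; 432/504 = 86% of the sampling window. This is a share of time, not of AUC. The documents give no concentration profile from which an AUC effect could be worked out.

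**6. What already applies to a missed sample**

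Protocol 7.4.2 and 7.4.3 and SAP 6.6.2 say how absent concentrations are treated. Protocol 5.4.1 and SAP 6.2 and 6.7 provide for checks of sampling times and listings at the review meetings. SAP Table 6.2: 1 has categories for unevaluable PK (E4) and for breaches of the time schedule (F5), and both PK sets exclude patients with important violations.

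**The case for a change.** The case for acting is that this is current text, that it stayed in place when the third amendment revised section 6.2.2.3, and that one word would cure it. A site that skipped the visit would comply with 6.2.2.3.2 and breach 6.1, so the status of the omission would be arguable. Category F5 gives no example, and SAP 6.3 does not say what complete PK data are. The loss would fall on the reference side only, would also weaken AUC0-∞, and would remove a time point from the descriptive laboratory comparison of the two cycles (Protocol 7.3.3).

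The wording conflict stands. The consequence does not follow. To reach it, a site would have to take a sentence from the section on later cycles, with no PK in its list, and let it override the cycle 2 section, the cycle 2 chart and section 6.1. The lack of a definition of completeness in SAP 6.3 exists whatever this sentence says, and is a separate matter. Asking for a report on any omitted sample would largely repeat the checks already planned.

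**Conclusion.** No change to the plan follows. The word in 6.2.2.3.2 is a clerical slip: the sentence's place in the protocol, section 6.1 and the flow-chart footnotes all put the option at cycle 3 onward. Correcting it would be editorial and would alter no endpoint, analysis set or estimate. The only size that can be given is plan arithmetic: 29 PK samples and 238.5 mL with the cycle 2 visits, 27 and 219.0 mL without. No effect on AUC0-tz is shown or derivable, and Cmax is unaffected.

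This rests on two assumptions. The first is that sites worked from the cycle 2 section and chart for cycle 2; nothing in the documents suggests otherwise. The second is that the four unclear chart cells are PK samples, which matters only for the Table 5:1 support and not for the conclusion.
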